## PROTOCOL SYNOPSIS

Study Title	Tantrum Tamers 2.0: The Role of Emotion
Funder	National Institute of Mental Health (R21MH113887)
Clinical Phase	N/A
Study Rationale	There is variability in standard of care Behavioral Parent Training (BPT) outcomes for early-onset (3 to 8 y.o.) Behavior Disorders (BDs), suggesting yet unidentified causal mechanisms. One candidate, emotion regulation (ER), has been implicated in the development of early-onset BDs. This study explores ER in the context of BPT.
Study Objective(s)	
Primary Describe child behavior and emotion regulatory processes in BPT.
 
Secondary Use preliminary results to inform future research on BPT adaptations.

Test Article(s) (If Applicable)	N/A
Study Design	Single-arm, open trial of Behavioral Parent Training (BPT) for early-onset behavior disorders (BDs)
Subject Population key criteria for Inclusion and Exclusion:	
Inclusion Criteria
 
 
1. 3-8 year old child
 
2. Parent is legal guardian
 
3. Child has clinically significant problem behavior
 
4. English-speaking
 
 
Exclusion Criteria
 
 
1. Parent current mood, psychotic, substance use disorder
 
2. Current involvement child protective services
 
3. Child developmental/physical disability precludes BPT
 

Number Of Subjects	45
Study Duration	
Each family: Approximately 12 weeks
 
All families: Approximately 2 years

Study Phases Screening Study Treatment Follow-Up	(1) Screening/Baseline : screening to determine eligibility and obtain consent and (2) Intervention : study intervention; 3) Post-assessment : repeat baseline measures.
Efficacy Evaluations	N/A
Pharmacokinetic Evaluations	N/A
Safety Evaluations	N/A

---

**Statistical And Analytic Plan**

Given pilot nature of study and small sample size, trends in the data will be examined, including means and standard deviations.

---

**DATA AND SAFETY MONITORING PLAN**

[name] responsible for data and safety monitoring. No data or safety issues emerged, but would have been/will be discussed with IRB and NIMH.

---

# **1 BACKGROUND AND RATIONALE**

## **1.1 Introduction:**

Eight-million (16%) U.S. children have a Behavior Disorder (BD), which is linked to a ten-fold increase in education, health care, and criminal justice costs. Early intervention is thus critical, yet outcomes for the standard of care, Behavioral Parent Training (BPT), vary suggesting the likelihood of a yet to be identified underlying mechanism. One likely candidate, emotion regulation (ER), has been implicated in a broad range of adult and child outcomes, including early-onset BDs. For example, parental difficulties with ER, as well as difficulties helping children to navigate and regulate emotion (i.e., emotion socialization), are linked to the etiology, maintenance, and severity of early-onset BDs. As such, this NIMH Exploratory and Developmental Research Grant (Parent R21) aims to further explore the ER in the context of BPT process and outcomes.

## **1.2 Name and Description of Investigational Product or Intervention:**

Behavioral Parent Training (BPT) is the well-established, standard of care treatment for early-onset BDs. Both a parent and the target child attend sessions which focus on parents learning, practicing and effectively using new skills to manage child behavior. Phase I skills focus on teaching parents to provide positive attention to behaviors they want to increase and Phase II focuses on improving child compliance by using effective and consistent consequences for noncompliance. Treatment is an average of 8-12 weeks. This study is exploring the mechanisms underlying BPT.

## **1.3 Non-Clinical and Clinical Study Findings:**

BPT is the recommend first line of treatment and standard of care for early-onset BDs. Therefore, the probability and magnitude of harm or discomfort anticipated in the research are not greater in and of themselves than those ordinarily encountered if families were seeking psychological services in the community. In turn, the benefit of improving child behavior outweigh risks.

## **1.4 Relevant Literature and Data:**

This is a pilot study, so it will serve as preliminary data for future work.

# **2 STUDY OBJECTIVE**

## **2.1 Primary Objective:**

Describe patterns of child behavior and emotion regulatory processes in BPT.

## **2.2 Secondary Objective:**

Use preliminary results to inform future research on BPT adaptations.

# **3 INVESTIGATIONAL PLAN (brief overview)**

## **3.1 Study Design:**

Single-arm, open trial of Behavioral Parent Training (BPT) for early-onset behavior disorders (BDs).  
Study phases: Screening/Baseline, Treatment, Post-treatment.

### **3.2 Allocation to Treatment Groups and Blinding (if applicable):**

N/A

### **3.3 Study Duration, Enrollment and Number of Subjects:**

N = 45 children;

Each child participates in BPT treatment with a parent for an average of 10 weeks (M = 8 to 12);

Total study time with screening and post-treatment assessment approximately 12 weeks/family.

### **3.4 Study Population:**

Inclusion Criteria: 3-8 year old child; Parent legal guardian; Child meets criteria for clinically significant problem behavior; English-speaking.

Exclusion Criteria: Parent has current mood, psychotic, substance use disorder; Current involvement child protective services; Child has developmental/physical disability that precludes BPT

## **4 STUDY PROCEDURES**

### **4.1 Screening/Baseline Visit procedures:**

Interested families contact study coordinator to determine eligibility and, if eligible, are scheduled for a baseline assessment to assess primary other study variables.

### **4.2 Intervention/Treatment procedures (by visits):**

Both a parent and the target child attend sessions which focus on parents learning, practicing and effectively using new skills to manage child behavior. Phase I skills focus on teaching parents to provide positive attention to behaviors they want to increase and Phase II focuses on improving child compliance by using effective and consistent consequences for noncompliance. Sessions recorded for therapist supervision and study purposes.

### **4.2 Follow- up procedures (by visits):**

Screening/baseline measures repeated at treatment completion.

### **4.3 Unscheduled visits:**

N/A

### **4.4 Concomitant Medication documentation:**

N/A

### **4.5 Rescue medication administration ( if applicable):**

N/A

### **4.6 Subject Completion/ Withdrawal procedures:** Completion determined by parent meeting established BPT skill mastery criteria. Parents unable to continue with treatment (e.g., moving), referred for other services/providers when possible.

#### **4.7 Screen failure procedures:**

Ineligible families referred to local providers who provide BPT (or other relevant psychological treatment for children).

### **5 STUDY EVALUATIONS AND MEASUREMENTS**

#### **5.1 Efficacy Evaluation ( if applicable):**

N/A

#### **5.2 Pharmacokinetic Evaluation ( if applicable):**

N/A

#### **5.3 Safety Evaluations:**

N/A

### **6 STATISTICAL CONSIDERATION**

#### **6.1 Primary Endpoint:**

Eyberg Child Behavior Inventory (ECBI; Eyberg & Pincus, 1999)

#### **6.2 Secondary Endpoint:**

Difficulties with Emotion Regulation Scale (DERS; Gratz & Roemer, 2004)  
Coping with Children’s Negative Emotions Scale (CCNES; Fabes et al., 2002)

#### **6.2 Statistical Methods:**

Given the pilot nature of the study and small sample size, trends in the data are focus of analyses, including means and standard deviations for aforementioned measures.

#### **6.3 Sample Size and Power:**

This is a pilot study with insufficient sample size and power to achieve statistical significance. Trends examined to inform sample size to achieve adequate power in future work.

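### The statement in section 6.3 that the study cannot reach statistical significance is too sweeping for 45 paired families, and the named outputs lack the SD of change or pre-post correlation that future sizing may need

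*Combined protocol and SAP*

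**What the plan says.** Section 6.3 (Sample Size and Power) states: "This is a pilot study with insufficient sample size and power to achieve statistical significance". It then gives the purpose of the results: "Trends examined to inform sample size to achieve adequate power in future work". No calculation accompanies either sentence.

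Section 6.2 (Statistical Methods) refers to the pilot nature of the study and its small sample, and says that "trends in the data are focus of analyses, including means and standard deviations for aforementioned measures". The measures are the ECBI (primary, section 6.1) and the DERS and CCNES (secondary). No change score is defined for any of them.

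The design is a single arm (section 3.1) with 45 children (section 3.3), each treated together with a parent. Section 4.2 (Follow-up procedures) says: "Screening/baseline measures repeated at treatment completion". Section 4.6 defines completion by the parent reaching skill mastery and foresees that some families will stop: "Parents unable to continue with treatment (e.g., moving), referred for other services/providers when possible". No dropout rate is given.

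**The concern.** Power is defined only for a given test, significance level, effect and number analysed. Section 6.3 asserts a power property with none of these, so a reader cannot tell which comparison it is about. With one group measured twice, the direct comparison on the primary endpoint is within child, and a paired comparison in 45 families is not obviously hopeless.

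The second matter is practical. If the results are to inform the size of a later study, the plan should name the quantities that such a calculation uses. Means and standard deviations describe the scores. They do not show how closely a child's second score follows the first, and that sets the variance of a change score or of a baseline-adjusted comparison. If the analysis stops at the named statistics, the pilot could end without a quantity it was meant to supply.

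**Working it through.** **The plan's own figure.** There is nothing to reproduce. The documents give N = 45 without derivation, and the power statement is in words only.

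**Inputs from the documents.** One arm (3.1); 45 children, read as one target child per family (3.3); the same measures at baseline and at treatment completion (4.2, Follow-up procedures).

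**Inputs assumed, because the documents give none.**
- Paired t test on change, two-sided 5%.
- Target power 80%, with 90% also shown.
- Mean change d from 0.2 to 0.8, in units of the SD of change.
- Complete pairs: 45, 40, 36 (0.80 × 45) or 30 (two-thirds of 45).

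**Step 1: power with 45 pairs.** Power = P(T > t₀.₉₇₅,ₙ₋₁), where T is noncentral t with n − 1 degrees of freedom and noncentrality d√n. The opposite rejection tail is negligible here and is left out.

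| d (SD of change) | 0.2 | 0.3 | 0.4 | 0.43 | 0.5 | 0.8 |
|---|---|---|---|---|---|---|
| Power, n = 45 | 26% | 50% | 75% | 80.5% | 91% | >99.9% |

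Cross-check by normal approximation: d at 80% power = (1.960 + 0.842)/√45 = 2.802/6.708 = 0.418, against 0.427 from the noncentral t.

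**Step 2: losses.** The 95% CI half-width for mean change is t₀.₉₇₅,ₙ₋₁/√n in units of the observed SD of change. For n = 45 this is 2.015/6.708 = 0.300. It is also the smallest observed mean change that gives p < 0.05.

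| Complete pairs | CI half-width | d at 80% power | d at 90% power | Power at d = 0.43 |
|---|---|---|---|---|
| 45 | 0.30 | 0.43 | 0.49 | 80.5% |
| 40 | 0.32 | 0.45 | 0.53 | 76% |
| 36 | 0.34 | 0.48 | 0.56 | 71% |
| 30 | 0.37 | 0.53 | 0.61 | 62% |

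**Step 3: other significance levels, n = 45.** Change detectable with 80% power is 0.38 SD at one-sided 5%, and 0.50 SD at two-sided 0.05/3 (one test for each of the three scales).

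**Step 4: units.** With equal SDs at both visits and pre-post correlation r, SD of change = SD × √(2(1 − r)). So 0.427 SD of change is 0.51, 0.43 or 0.33 baseline SD for r = 0.3, 0.5 or 0.7.

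**Step 5: why means and SDs fall short for sizing.** Variance of change = SD₁² + SD₂² − 2r·SD₁·SD₂, so the SDs at the two visits do not determine it without r. With equal SDs it is 2(1 − r)SD²: 1.4 SD² at r = 0.3 and 0.6 SD² at r = 0.7. For a fixed raw difference, the sample needed in a paired study is proportional to this variance, so the two values of r give sizes that differ by 1.4/0.6 = 2.3-fold. For a baseline-adjusted comparison the factor is 1 − r²: 0.91 against 0.51, a ratio of 1.8. These values of r are illustrations; the documents give none.

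**The case against.** The strongest reply is that 6.3 may be right for the question the investigators have in mind. No effect size is stated. If a change of 0.2 to 0.3 SD mattered, power would be 26% to 50% and the word insufficient would be apt. The rationale also concerns emotion regulation as a mechanism, not only mean change in behavior. If the question were a correlation between emotion regulation and outcome (an assumption, since no such analysis is specified), 45 pairs would give about 52% power at a correlation of 0.3 and reach 80% only near 0.41 (Fisher z, two-sided 5%). Losses add to this: the second assessment is tied to treatment completion, so families who stop may contribute no pair. All of this stands. A reader might infer from Step 1 that the sentence in 6.3 is simply false. The documents do not support that, because they set no target effect against which it could be false.

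A reader might also infer that 6.2 excludes within-child change, or that the power statement is what led to a descriptive analysis. Neither is in the text. Section 6.2 introduces means and SDs as included in the analysis, so change is unspecified, not ruled out. Its stated reasons are pilot status and small sample size, not the claim in 6.3.

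Finally, the analysis is descriptive, no test is planned and no decision depends on 6.3. That limits the importance of the point. It does not answer the gap between the named outputs and the purpose given in 6.3, although a future study sized only on post-treatment scores could manage with the post-treatment SD.

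**Conclusion.** The point holds in limited form. The power statement is unqualified and unsupported. For mean within-child change it is untrue at moderate or larger effects: 80% power at 0.43 SD of change with 45 complete pairs, and at 0.53 SD with 30. It is fair for changes of 0.2 to 0.3 SD. These figures rest on an assumed two-sided 5% paired t test and assumed numbers of completers.

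The more useful part is the reporting gap. The named statistics do not include the SD of change or the pre-post correlation, and sizing a paired or baseline-adjusted future study needs one of them.

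Power to detect pre-post change should not be read as power to show that treatment works. With a single arm, a significant change would not establish a treatment effect. The point is modest in weight, but worth correcting because the correction is nearly free.

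**What to change.** In section 6.2 (Statistical Methods), add for ECBI, DERS and CCNES: the mean within-child change with its two-sided 95% CI, the SD of change, the pre-post correlation, and the number of complete pairs behind each.

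In section 6.3, replace the first sentence with a precision statement, for example:

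> With 45 complete pairs, the two-sided 95% confidence interval for mean within-child change has a half-width of about 0.30 SD of change (0.37 with 30 pairs). The study is not powered for small changes or subgroup comparisons, and pre-post change in a single arm does not establish a treatment effect.

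The sentence on informing future sample size can stay. The cost is a few lines of wording and a few more statistics from assessments already planned, with no extra families or visits.

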#### **6.4 Interim Analysis:**

N/A

### **7 STUDY INTERVENTION (drug, device or other intervention details)**

Behavioral Parent Training is the recommend first line of treatment and standard of care for early-onset BDs. Both a parent and the target child attend sessions which focus on parents learning, practicing and effectively using new skills to manage child behavior. Phase I skills focus on teaching parents to provide positive attention to behaviors

they want to increase and Phase II focuses on improving child compliance by using effective and consistent consequences for noncompliance.

## **8 STUDY INTERVENTION ADMINISTRATION (if applicable)**

Single-arm, open trial of well-established, evidence-based intervention (BPT), so no randomization or blinding.

## **9 SAFETY MANAGEMENT**

Data safety monitored throughout course of study (see Data Collection and Management).

Given that BPT is a well-established intervention, Adverse Events extremely unlikely.

No Adverse Events occurred.

## **10 DATA COLLECTION AND MANAGEMENT**

- All families assigned study identification number (Family ID).
- Identifying information maintained for contacting families for study purposes only.
- Identifying information stored separately from study data, which is coded by Family ID.
- Study data stored on password protected server with 2-step verification and limited to study staff.
- All hard copies stored in locked, passcode protected laboratory space.

## **11 RECRUITMENT STRATEGY**

Families recruited from local community and agencies serving young children.

Methods included flyers, advertisements, and word-of-mouth.

Interested families contact study coordinator to do initial eligibility screen.

## **12 CONSENT PROCESS**

Parental consent for self and child at baseline assessment.

Consent included a description of study procedures, benefits, and risks.

Assessor also reviewed consent with parent and addressed any questions/provided additional information .

## **13 PLANS FOR PUBLICATION**

Given preliminary nature of data, results will be published in a primary outcomes paper (e.g., brief report) as well as serve as pilot data for a subsequent grant.

**15 APPENDIX**  
N/A
